This proposal involves two studies of evidence-based suicide prevention practices triggered by CareSource justice notifications, in a 2x2 factorial design. The **first study** will randomize CareSource's ~43,000 Ohio subscribers who pass through jails over 12 months to receive monthly Caring Contact letters sent by CareSource over a 6-month period or to Care as Usual. The **second study** (running simultaneously) will involve a subset of ~6,000 of the 43,000 subscribers passing through jail who were seen in one of 12 large BH agencies in the 6 months prior to jail detention. Using a stepped wedge design, the 12 agencies will be brought online over time, receiving (a) notifications of jail detentions/releases with instructions for re-engaging clients in services; and (b) training in the Safety Planning Intervention plus notification to use it when a subscriber with past *medically treated* suicide attempts (identified by CareSource through claims data) is released from jail.

Specifically, we plan to examine the following:

Aim 1: Evaluate the effectiveness of the implemented study interventions.

Hypothesis 1a: CareSource subscribers who receive CC letters during the 6-month period will have fewer claims related to suicide attempts than subscribers who did not receive CC letters.

Hypothesis 1b: Provider involvement in the reports, re-engagement, and training (RRT) intervention will be associated with a reduction in subscriber claims related to suicide attempts. Further, the addition of flags and recommendations to provide SPI for individuals with past 12 months claims data identified suicide attempts will further reduce suicide attempts.

Aim 2. Examine the number of outpatient behavioral health claims in the 6 months following the index jail release and number of calls to CMS line as mediators of the intervention/s effects on suicide attempts. Mediation will be revealed by the extent to which the intervention effect parameter estimates change with the addition of the putative mediator. We will use bootstrap methods to estimate 95% uncertainty intervals around the mediated effect.

Aim 3. Examine intervention cost-effectiveness and return on investment. We will examine costs (and savings) in future years for both the Caring Contacts and Reports, Re-engagement, and Training (RRT) components of the proposed study.

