Provider meetings: BH providers who are participating in the RRT Intervention (N=120) will be asked to participate in monthly meetings with the Study PIs and CareSource to talk about their experiences, offer feedback, and help problem-solve challenges. These meetings will be held virtually. Additional personnel, including clinical directors, business managers, and other relevant staff may attend these meetings. These meetings are intended to provide an opportunity for the site to ask us questions, address concerns, work through challenges, etc. Because part of this study is focused on implementation, we will need to have formal review and ratings of the information provided in the meetings. CareSource will record the meetings and provide transcripts of the discussions for analysis. Due to the variation in staff attending the steering team meetings, verbal consent will be obtained prior to the start of each of these meetings. If verbal consent is not received, the meeting will not be recorded/transcribed.

Study Outcomes: All study outcomes will be tracked through the use of claims data. These data include diagnosis, treatment, and billed and paid amounts. Data will be extracted using previously established algorithms for suicide and self-injury research developed by the Mental Health Research Network. This is not medical record data. We will not have access to the patient's health record. CareSource will extract data from their Jail-Medicaid database to examine billing and insurance claims submitted for visits associated with our study suicide-outcomes of interest (suicide attempts, all cause injury and poisoning, outpatient BH visits, calls to CMS line, suicide-related ED visits/hospitalizations, and returns to jail detention).

Training behavioral health providers: The 12 BH agencies who see the largest number of justice-involved CareSource subscribers (approx. 6,000 total annually) will be randomly assigned to four cohorts. All four cohorts will follow the same intervention protocols, but they will begin at Months 4, 6, 8, and 10 of the CC intervention, respectively. As BH agencies are assigned to the RRT condition, they will receive training in reaching out to and re-engaging clients who pass through the justice system, and training in suicide risk assessment (C-SSRS²⁸) and response (SPI²⁹).

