Training will use Stanley and Brown's well-established methods for videoconference training. SPI and C-SSRS training take about 6 hours total. Prior to the training, individuals will be emailed the SPI manual used in a previous intervention trial (SPIRIT).^{29,46} On the day of the training, information on the rationale for SPI, an overview of SPI, and the steps of SPI, with video clip demonstrations interspersed will be presented. We will provide an additional 30 minutes of training in reaching out to and re-engaging justice-involved individuals in BH care. After completing the online training and study of the written SPI manual, counselors will receive a 2.5 hour live training in SPI fidelity rating via webcam (i.e., it is live, but not in person). The group views and rates fidelity of SPI videos that vary in quality, and then discusses their answers. Drs. Stanley and Brown have found that practicing SPI fidelity assessment by critiquing SPI helped learners understand the SPI model and commit it to memory. C-SSRS training also includes video and live practice. These trainings will be recorded to ensure fidelity and consistency across the trainings. The audio/video files recorded during the meeting will be downloaded onto secure servers at Butler and Michigan State University (MSU).

Weekly reports: During the months BH agencies are assigned to the RRT intervention condition, they will receive weekly reports from CareSource with notifications of jail booking/release dates of any client seen by the agency in the 6 months prior to arrest. Reports will include instructions for how to reengage the client, and a reminder that the C-SSRS can be used for suicide risk assessment. Subscribers with any past (lifetime) suicide attempt documented in available claims data will be flagged for additional outreach and action, including SPI. These reports will be built into an existing, automated CareSource system that

sends jail booking/release data to BH agencies. This system is currently being piloted and refined by CareSource.

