For Aim 1, we will assess total number of subsequent attempts using the already-developed Mental Health Research Network (MHRN) algorithm for extracting MT suicide attempt information from claims data.^{10-12,48-58} The main effectiveness analysis is planned as a comprehensive model (i.e., including all 43,000 subscribers) evaluating Study 1 and Study 2 intervention effects, which provides optimal power and the ability to test interactive effects of interventions. All analyses will covary baseline (i.e., past year) values of dependent variables, and will use days incarcerated in the 6 months after the index jail release as an offset. **MT suicide attempts.** The main analysis framework will be logistic regression with the cumulative risk of a claims-data-identified suicide attempts requiring medical treatment over six months post-release as the outcome. We will secondarily use a negative binomial model and a count outcome for the number of MT suicide attempts. Our models will include robust standard errors due to clustering at the agency level. We will adjust for study month, and include indicator variables reflecting: (1) Study 1 intervention condition (i.e., CC or CAU); (2) inclusion in Study 2; (3) Study 2 intervention condition (i.e., RRT or Control). The ***hypothesis that the Study 1 intervention (CC) reduces suicide attempts*** is evaluated with magnitude and significance of parameter estimate associated with random assignment to the Study 1 intervention. The ***hypothesis that the Study 2 intervention (RRT) reduces suicide attempts*** is tested with the parameter estimate associated with exposure to the level 2 intervention. ***The hypothesis that the addition of flags and recommendations to provide SPI*** for individuals with past 12 months claims data identified suicide attempts (one component of the Study 2 intervention) ***will further reduce suicide attempts*** will be tested through the interaction between past history of suicide attempt and being in the Study 2 intervention condition. Identical analyses will be conducted for the other outcomes (all count outcomes): all cause injury and poisoning, outpatient BH visits, calls to CMS line, suicide-related ED visits/hospitalizations, and returns to jail detention. ***Exploratory.*** We will evaluate the interaction of Study 1 and Study 2 interventions by including an interaction term of the two indicators. ***Moderators.*** We will test sex, race/ethnicity, past suicide attempt (y/n), past 6-month BH visit (y/n), past 12-month arrest (y/n), area Deprivation Index,⁵⁹⁻⁶⁰ Mental Health Professional Shortage Area (HPSA)

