
score,⁶¹⁻⁶² and per capita incarceration (by zip code) as moderators of intervention effects on suicide attempts, using $p < .01$.

Aim 2 will be analyzed by examining the number of outpatient BH claims in the 6 months following the index jail release and number of calls to the CMS line as mediators of the intervention/s effects on suicide attempts by adding this variable to our effectiveness model. Mediation is revealed by the extent to which the intervention effect parameter estimates change with the addition of the putative mediator. We will use bootstrap methods to estimate 95% uncertainty intervals around the mediated effect.

For Aim 3, our grants accounting will capture the costs of the CC mailings. Treatment received as part of the intervention and CAU conditions (including outpatient, inpatient, and ED mental health and suicide-related medical care visits) will be tracked using claims data. Costs of CAU will be computed as CareSource payments plus co-pay and deductibles. We will add training costs for providers but exclude other research costs that would not be incurred if RRT was standard care. The primary cost-effectiveness (CE) measure, computed from a societal perspective for each intervention arm, will be the program cost divided by the sum of suicide attempts prevented. We also will assess the net cost of the program from a MCO perspective. That measure will exclude patient payments from costs.

Costs (and savings) in future years will be discounted to present value in the year of jail release using the 3% discount rate recommended by the Second Panel on Cost-Effectiveness in Health and Medicine.⁶³ We will bootstrap the 95% uncertainty interval around the CE ratio. Analyses from the MCO perspective will compute the change in claims costs by running a generalized linear model (GLM) with gamma, inverse Gaussian, or Poisson variance based on data distribution, the log link function, and robust standard errors.⁶⁴ We will use a 2-part GLM unless less than 5% of patients have zero costs. Independent variables will include treatments received, demographics, Elixhauser co-morbidities,⁶⁵ and days of MCO coverage after jail discharge. We also will track the MCO separation rate post-discharge by group.

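### The RRT-by-past-attempt interaction isolates the SPI flag only if the rest of RRT has the same odds ratio in past attempters and others, which the plan neither states nor can check

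*Combined protocol and SAP*

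**What the plan says.** Section 2.A, Hypothesis 1b, makes two claims. The first is that RRT reduces attempts. The second concerns "the addition of flags and recommendations to provide SPI", expected to lower attempts further among clients whose claims show an attempt in the past 12 months. Section 2.C4 repeats the second claim, describes the flag as one component of the Study 2 intervention, and says that the hypothesis "will be tested through the interaction between past history of suicide attempt and being in the Study 2 intervention condition".

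Section 2.C2 explains how the flag is delivered. Under Weekly reports: "During the months BH agencies are assigned to the RRT intervention condition, they will receive weekly reports from CareSource", and "Subscribers with any past (lifetime) suicide attempt documented in available claims data will be flagged for additional outreach and action, including SPI". Under Training behavioral health providers, the 12 agencies are randomised to four cohorts that start at Months 4, 6, 8 and 10 under one common protocol. When an agency crosses over, "they will receive training in reaching out to and re-engaging clients who pass through the justice system", together with training in C-SSRS and SPI.

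The moderator paragraph of Section 2.C4 lists attempt history again: "We will test sex, race/ethnicity, past suicide attempt (y/n), past 6-month BH visit (y/n" and further variables are to be examined "as moderators of intervention effects on suicide attempts, using" p < .01. The power paragraph uses a two-sided 5% level and gives 96.4% power for an odds ratio of 0.63 in Study 2 subscribers with a past-year attempt.

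**The concern.** A claim that one component adds something beyond the rest of a package needs people who get the rest without that component, or an assumption that stands in for them. Here the flag starts at the same agency step as the reports, the re-engagement instructions and the training. Within RRT months, attempt history alone decides who is flagged. Every past attempter exposed to RRT is flagged, so nobody shows what the rest of RRT does in past attempters without the flag.

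At stake is the reading of a named Aim 1 hypothesis. If re-engagement works better in people with a previous attempt, the term falls below 1 with no contribution from the flag. If it works less well in them, a real flag effect can be hidden. A larger sample would estimate the same mixture more precisely without separating its parts.

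**Working it through.** **1. The plan's own figure.** The only power figure near this hypothesis is 96.4%, for an odds ratio of 0.63 in about 600 subscribers (10% of 6,000). The stated risk with a past-year attempt is 0.204: odds 0.204/0.796 = 0.256, times 0.63 = 0.161, giving a risk of 0.139. Half of cohort-months are in RRT: (9 + 7 + 5 + 3)/48 = 24/48. A standard two-proportion calculation, 300 v 300, 0.204 v 0.139, two-sided 5%, gives 56.0%, so 96.4% is not reproduced. The plan's simulation code is not in the documents, and the point below does not depend on this gap. What matters here is that 96.4% is worded as power for an effect within the past-attempt stratum, not for the interaction that is to test the hypothesis.

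**2. What the interaction estimates.** Let X = 1 in RRT and H = 1 for a past attempt. Let φ be the odds ratio of the flag, and ρ1 and ρ0 the odds ratios of the rest of RRT in past attempters and in others. If the flag is given exactly to those with H = 1 in RRT:

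- RRT odds ratio in past attempters = ρ1 × φ
- RRT odds ratio in others = ρ0
- interaction odds ratio = φ × (ρ1/ρ0)

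The data supply two stratum odds ratios for three unknowns. Equivalently, the flag indicator equals X × H, so the columns 1, X, H, X × H and flag have rank 4, not 5. The interaction equals φ only if ρ1 = ρ0.

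**3. Different truths, same result.** The first two rows use the plan's 0.63 and 0.87, with 0.63/0.87 = 0.724. The component effects in all rows are assumptions, chosen only to show the algebra. The last column is from 600 stepped-wedge simulations per row (12 agencies, starts at Months 4/6/8/10, month and agency effects, ICC 0.01, risks 0.034 and 0.204).

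| Truth | φ | ρ1 | ρ0 | φ × ρ1/ρ0 | Simulated median (share p < .05) |
|---|---|---|---|---|---|
| Flag works, rest of RRT equal | 0.724 | 0.87 | 0.87 | 0.724 | 0.71 (19%) |
| No flag effect, rest of RRT stronger in past attempters | 1 | 0.63 | 0.87 | 0.724 | 0.72 (22%) |
| Flag works, rest of RRT weaker in past attempters | 0.724 | 1.0 | 0.724 | 1.00 | 0.96 (6%) |

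The first two rows cannot be told apart. The third hides a flag effect as large as that in the first.

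**4. Is the flag the same as the analysis variable?** The passages differ:

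- Section 2.C2, Weekly reports: any lifetime attempt in available claims triggers the flag.
- Section 2.A and the hypothesis clause of Section 2.C4: attempts in the past 12 months.
- Section 2.C4, opening: 12 months of pre-arrest history are extracted.

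With a 12-month analysis variable, clients in RRT months with only older attempts are flagged but counted among the others. The exact identity in step 2 then fails, because the comparison stratum contains some flagged people. This does not restore identification. The flag is still RRT × lifetime history, so its effect remains mixed with any modification of the rest of RRT by that history. The documents do not give the share with only older attempts, so the dilution cannot be sized.

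**5. Power of the interaction, for context.** With subgroup odds ratios 0.63 and 0.87, and groups of 300, 300, 2,700 and 2,700, the variance of the log ratio is 0.0205 + 0.0279 + 0.0113 + 0.0129 = 0.0725, so SE = 0.269. Then |ln 0.724|/0.269 = 0.323/0.269 = 1.20, and power is about 22% (two-sided 5%, clustering ignored).

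**The case against.** The strongest reply is that the term is a valid test of the flag if the rest of RRT has one common odds ratio, and that the plan openly calls the flag a component of a package. The first part stands. A reader might infer that the hypothesis cannot be tested at all, and the documents do not support that: the term is estimable and tests the flag under a strong assumption. Disclosing the package does not supply the assumption, and the moderator list treats its failure as possible.

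Other stronger readings also fall short:

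- **Two explicit thresholds.** No alpha is set for this test. The 5% level appears only in the power paragraph. The moderator list covers both interventions and gives no time window for past attempt. This is an overlap to clarify, not a stated contradiction.
- **SPI reaching unflagged clients biases the term.** All RRT providers are trained in SPI, so this may happen. But the hypothesis concerns "the addition of flags and recommendations to provide SPI", that is, the prompt on top of training, and a smaller interaction would then be a fair answer about the prompt.
- **Past attempt × CC shows how RRT is modified.** How mailed letters work by attempt history says little about how provider re-engagement does.
- **Worked examples show likely harm.** They rest on assumed effects. Examples built on equal absolute benefit show the additive-versus-multiplicative scale issue of any logistic interaction, which would remain if the flag were randomised separately.

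**Conclusion.** The concern holds as a limit on interpretation. The planned interaction measures whether the effect of the whole RRT package differs by attempt history. Reading it as the added effect of the flag or SPI prompt requires ρ1 = ρ0, which is unstated and cannot be checked in a design where no past attempter receives RRT without the flag. The error in a flag conclusion is the factor ρ1/ρ0, for which the documents give no value. The conclusion rests on the flag travelling only in RRT-month reports, being set by history, and being common to all cohorts, as Section 2.C2 says. The CC comparison, the overall RRT comparison and the RRT effect within the past-attempt stratum, read as a package effect, are not touched by this point.

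**What to change.** 1. Reword the second sentence of Hypothesis 1b and the matching clause of Section 2.C4: the interaction tests whether the effect of the full RRT package differs by past-attempt history.
2. State that the added effect of the flag/SPI prompt is not isolated, and that reading the term as that effect would require the rest of RRT to have equal odds ratios in both strata.
3. Report the RRT effect within the past-attempt stratum as a package effect, as an odds ratio and a risk difference.
4. Reconcile the lifetime flag definition with the 12-month hypothesis, analysis variable and data extract, so that the stratum is built in the same way for control and RRT periods.
5. State one threshold for RRT × past attempt, and keep past attempt in the p < .01 moderator list for CC only.

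The cost is wording and one extra table, plus a possible change to the data extract depending on how item 4 is settled. The downside is that the sponsor gives up a component-level claim, but the design does not support that claim.

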Using the IHI Framework for Going to Full Scale,⁶⁶⁻⁶⁷ this project will focus on sustainability and scalability. We will assess, maximize, and optimize intervention: (1) scalability (per the Intervention Scalability Assessment Tool⁶⁸); (2) sustainability (per the Program Sustainability Assessment Tool⁶⁹⁻⁷⁰) (3) feasibility, acceptability, and appropriateness to providers and systems (per the Acceptability of Intervention Measure,⁷¹ Intervention Appropriateness Measure,⁷¹ and Feasibility of Intervention Measure⁷¹); and (4) actual and recommended implementation strategies (via process mapping and implementation process/case notes).

Statistical power. Assumptions. We conducted a simulation study, allowing for variability in release dates, numbers eligible, and introducing a small intra-cluster correlation (ICC = .01). We assumed 43,000 eligible subscribers for Study 1, with 50% randomly assigned to CC. Based on last year's data, we assumed 6,000 eligible subscribers for Study 2. We expect that ~10% of the 6,000 ($n \sim 600$) will have past suicide attempt identifiable through CareSource claims data. We assumed a six-month risk of suicide attempt 0.05, but past 12-month claims data-identified suicide attempt increases this risk (i.e., .034 in absence of past-year suicide attempt, 0.204 with a past-year suicide attempt, odd ratio (OR) = 5), similar to SPIRIT. **Results.** We ran the simulation model 2001 times. Significance was assessed using a two-tailed type-I error level of 5%. Caring Contacts. We will have 85.6% power to detect an effect equivalent to an OR of 0.89. CC has been found to have much stronger effects than this in previous studies²² suggesting that we are adequately powered for CC. RRT. If we assume an intervention effect for Study 2 of 0.87 OR, we will have 88.3% power to detect this effect. For subscribers with a past year suicide attempt within Study 2 (who will be flagged to receive SPI), we will have 96.4% power to detect an OR of 0.63 (the OR detected for SPI in our previous trial, SPIRIT).⁴⁶ Having superadequate power for this test offsets concerns about providers potentially not providing SPI as instructed in this large, real-world study.

D. Material Inducements

Study 1

Provider focus groups: No material inducements will be provided for BH providers who engage in the focus groups. Providers will complete study-related procedures during work time and are typically not able to accept material inducements.

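### The SPI test (RRT × past attempt) is specified without a Study 2 inclusion × past-attempt term, so a difference in past-attempt slope between agency clients and the roughly 37,000 other subscribers would be read as an RRT effect

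*Combined protocol and SAP*

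**What the plan says.** All of this is in the Combined protocol and SAP.

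- **Population.** The Aim 1 paragraph of section C4 plans "a comprehensive model (i.e., including all 43,000 subscribers"), covering both studies at once.
- **Listed terms.** The model adjusts for study month and will "include indicator variables reflecting: (1) Study 1 intervention condition (i.e., CC or CAU); (2) inclusion in Study 2; (3) Study 2 intervention condition". Past-year attempt enters as a main effect through the rule that "All analyses will covary baseline (i.e., past year) values of dependent variables".
- **SPI test.** The claim that flags and SPI recommendations add benefit "will be tested through the interaction between past history of suicide attempt and being in the Study 2 intervention condition". This is the second half of Hypothesis 1b (Specific Aims).
- **Exploratory test.** CC and RRT are tested for interaction "by including an interaction term of the two indicators".
- **Moderators.** The same section lists moderators of intervention effects, tested at p < .01. They include past attempt and a behavioural health visit in the past 6 months.

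The section names neither inclusion × past attempt nor inclusion × CC, and it does not restrict either test to Study 2. Study 2 subscribers are those seen at one of 12 large agencies in the 6 months before detention. What is randomised is the month in which each agency starts RRT (section C2).

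**The concern.** RRT can equal 1 only inside Study 2. An RRT × past-attempt term therefore gives RRT-exposed agency clients their own past-attempt slope, while everyone else shares another. Everyone else means Study 2 controls plus all outsiders. The inclusion main effect lets the overall risk of agency clients differ from that of outsiders, but it does not let their past-attempt slope differ.

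Only the contrast with Study 2 controls is protected by the random start times. The contrast with outsiders compares people in recent agency care with people who mostly were not. If past attempt predicts new attempts more weakly in agency clients, the model reports an SPI benefit that does not exist. If it predicts more strongly, the model reports harm or hides a real benefit. A named Aim 1 hypothesis could be answered wrongly in either direction. Agency-level robust standard errors change the variance, not this bias.

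**Working it through.** **The plan's own figure.** The plan gives no power for the interaction. The nearest figure is 96.4% for an odds ratio of 0.63 among flagged Study 2 subscribers. A two-proportion calculation with 300 versus 300 gives 56.0%, and simulation gives 52–54%, so it was not reproduced. The sponsor's simulation is only partly described, so this does not prove an error, and nothing below depends on it.

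**Inputs from the Statistical power paragraph and section C2**
- 43,000 in total and 6,000 in Study 2, so 43,000 − 6,000 = 37,000 outsiders.
- About 10% of Study 2 with a past attempt (about 600).
- Six-month risk 0.034 without and 0.204 with a past-year attempt. These risks imply an odds ratio of (0.204/0.796)/(0.034/0.966) = 7.28, although the text states 5.
- RRT starts at months 4, 6, 8 and 10. Exposed months are 9 + 7 + 5 + 3 = 24 of 48, or half. That gives about 3,000 exposed and 3,000 control, with 300 flagged in each.

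**Assumed, because the documents are silent:** outsider past-attempt prevalence of 3% or 10%, and different past-attempt odds ratios inside and outside Study 2.

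**Who sets the reference slope.** Of the 40,000 subscribers not exposed to RRT, 37,000/40,000 = 92.5% are outsiders. The information on a past-attempt log odds ratio is I = 1/[1/(n₁p₁q₁) + 1/(n₀p₀q₀)], with subscript 1 for past attempt and 0 for none. At equal slopes (odds ratio 7.28), the outsiders' share is 92.5% at 10% prevalence, 83% at 3% and 65% at 1%.

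**Expected bias with no SPI effect.** The false log ratio is about w × ln(OR inside / OR outside), where w is the outsiders' share of the reference information.

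Take 5 inside and 7.28 outside:
- Inside, risk with a past attempt is 0.150. Each Study 2 arm has I = 1/(1/38.2 + 1/88.7) = 26.7.
- ln(5/7.28) = −0.376.
- At 10% outsider prevalence, outsider I = 1/(1/600.8 + 1/1,093.7) = 387.8, so w = 387.8/414.5 = 0.936. Bias = −0.352, an odds ratio of 0.70. SE = √(1/26.7 + 1/414.5) = 0.200. Rejection for benefit = Φ(−1.96 + 0.352/0.200) = 42%.
- At 3%, outsider I = 156.3 and w = 0.854. Bias = −0.321, an odds ratio of 0.73. SE = 0.207 and rejection is 34%.

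The same formula for other assumptions:

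| Past-attempt OR inside / outside | True ratio | Apparent ratio (10%; 3% prevalence) | Rejection for benefit |
|---|---|---|---|
| equal | 1.00 | 1.00; 1.00 | nominal |
| 5 / 6 | 1.00 | 0.84; 0.86 | 13%; 11% |
| 5 / 7.28 | 1.00 | 0.70; 0.73 | 42%; 34% |
| 7.28 / 5 | 1.00 | 1.41; 1.35 | about 0 (errs towards harm) |
| 7.28 / 5 | 0.72 | 1.02; 0.98 | 2%; 3% |

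**Simulation check.** In 1,000 trials per scenario (month effects, model-based standard errors, incarceration-days offset left out), r denotes the inside odds ratio divided by the outside one. At 10% outsider prevalence, two-sided rejection of a true null was:
- 4.3% at r = 1.0
- 7.0% at r = 0.9
- 21% at r = 0.8
- 39% at r = 0.7

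At 3% prevalence and r = 0.7 it was 28%. With an ICC of 0.01 (10% prevalence, r = 0.7) it was 41%. With inclusion × past attempt added, the mean ratio was 0.98–1.03 and rejection 4–6% in every null scenario.

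**CC × RRT.** CC is randomised inside and outside Study 2, so only a different CC effect in agency clients matters. If the CC odds ratio is 0.89 outside and 1.0 inside, the false ratio is about exp(0.925 × ln(1/0.89)) = 1.11. If the CC odds ratio inside is 0.9 or 0.8 times that outside, simulated false rejection is 8.6% or 18%. With inclusion × CC added it is 3.5–5.4%.

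**The case against.** **The plan omits the term but does not exclude it.** Section C4 gives no full interaction equation, and the power paragraph describes the SPI target as lying within Study 2. A reader might infer that the sponsor has decided against the inclusion term. The text does not support that. It does support saying that an analyst who fits only the listed terms gets the contrast described here.

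**The size is assumed.** A reader might take 7.28 and 5 as the plan's values for two populations. They are not: both come from one sentence, where the stated risks and the stated odds ratio for the same parameter disagree. The heterogeneity is an assumption, and at a ratio of 0.9 the damage is small.

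**The direction is unknown.** A reader might infer that the SPI test is set to give a false benefit. The documents give no reason to prefer that sign.

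**The 0.72 benchmark is not the plan's.** It is 0.63/0.87, and the plan states no interaction target. If 0.87 is an overall effect that includes flagged clients, the ratio would be nearer 0.61.

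**Pooling buys power.** The sponsor pools for that reason. If the slopes are equal, the smaller standard error is legitimate. That stands, but it makes the test's validity depend on an unstated equality between groups that were not randomised.

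**Robust standard errors have their own problem.** In a check with uncorrected robust errors on 12 agencies and no ICC, rejection was 8–10% even with the added term, and 9% for the model as written with equal slopes. The 4–6% above holds for model-based errors only.

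**Scope.** CC × RRT is labelled exploratory and the moderators have a stricter threshold, so neither carries the weight of the SPI test.

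**Conclusion.** The concern holds for the SPI half of Hypothesis 1b. The listed model attributes any agency-versus-outsider difference in past-attempt slope to RRT × past attempt, because outsiders supply most of the reference information (65–92.5% for prevalences of 1–10%).

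The bias is nil at equal slopes and takes either sign otherwise. Under the assumed contrasts it ranges from modest (11–13% false rejection at 6 versus 5) to as large as the 0.72 yardstick (0.70–0.73, with 28–42% rejection across the analytic and simulated results). With the odds ratios swapped, it can cancel a real benefit of that size. These figures rest on assumed outsider slopes and prevalence, model-based standard errors and no incarceration offset.

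The point should be settled before analysis because it decides what a named hypothesis test estimates. The same gap in CC × RRT and the RRT moderators is secondary. Nothing here bears on the main-effect tests of CC or RRT.

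**What to change.** In the Aim 1 paragraph of section C4:

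1. State that the SPI test includes Study 2 inclusion × past attempt alongside RRT × past attempt. Fitting the SPI test in the Study 2 subset is an alternative but not an identical one: it also estimates month effects within Study 2, whereas the pooled model takes them mostly from outsiders.
2. Add Study 2 inclusion × CC to the exploratory CC × RRT test.
3. Add inclusion × moderator for each RRT moderator that varies within Study 2. Drop the past 6-month behavioural health visit as an RRT moderator. Study 2 membership requires such a visit, so that interaction is essentially not estimable.

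**Cost.** This needs a short text change and no change to conduct or data. The SPI interaction standard error rises from about 0.20 to 0.27–0.28; with 5 inside Study 2, √(2/26.7) = 0.27. Simulated power for a true ratio of 0.72 at equal slopes falls from about 36% to 25%, and for 0.63 from 58% to 41%. The lost precision was valid only under equal slopes. The plan should state power for the interaction itself.

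The change removes this bias only. It does not address the small number of agency clusters behind the robust standard errors.
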